1 INTRODUCTION

1.1 STUDY DESIGN

This is an international, multicenter, randomized, double-blind, placebo-controlled, two-stage study in adult participants at risk of rapidly progressive Autosomal Dominant Polycystic Kidney Disease (ADPKD) aged 18 to 50 years in Stages 1 and 2. In addition, Stage 2 also includes participants aged 18 to 55 years with a screening estimated Glomerular Filtration Rate (eGFR) between 30 and 44.9 mL/min/1.73 m².

The study is divided into 2 stages:

Stage 1: an up to 30-days screening period including a 2-week placebo run-in (to identify participants who are unlikely to follow the assigned treatment regimen), followed by a randomized, double-blind, comparative placebo-controlled core treatment period of 24 months duration.

After run-in, eligible participants, aged 18 to 50 years with an eGFR in (45 to 89.9) are randomized with a 1:1:1 ratio to placebo, 8 mg venglustat, or 15 mg venglustat.

Participants are stratified based on their predicted ADPKD progression rate (1C versus 1D versus 1E) according to Mayo Imaging Classification and geographical region (North America, Europe, China, Republic of Korea, Rest of the World).

After the interim unblinded aggregate safety review by the DMC of the first 150 randomized participants from Stage 1 having completed at least 1 month of treatment (or have prematurely discontinued), the DMC determined that the 15 mg dose was the highest dose to be safe and well tolerated in Stage 1, and recommended the venglustat 15 mg dose for Stage 2.

Stage 2: starts with an up to 30-day screening period including a 2-week placebo run-in (to identify participants who are unlikely to follow the assigned treatment regimen), followed by a randomized, double-blind, comparative core treatment period of 24 months duration. After run-in, eligible participants aged 18 to 55 years with an eGFR of 30 to 89.9 are randomized with a 1:1 ratio to placebo and 15 mg venglustat. Participants are stratified based on their predicted progression rate (1C versus 1D versus 1E) according to Mayo Imaging Classification and geographical region (North America, Europe, China, Republic of Korea, Rest of the World).

Participants who completed 24 months of treatment in EFC15392 study may be given the option to enroll into an open-label long-term extension study LTS15823 (additional 24 months of treatment with 15 mg venglustat).

As per protocol a first step analysis was planned when all participants from Stage 1 have been randomized and have completed the Month 18 visit (or have discontinued the study) for the submission to the accelerated approval. Then a second step analysis was planned to be conducted after study completion of Stage 1 and Stage 2 participants.

Considering the decision after futility analysis to discontinue the study, the two-step analysis is no more applicable. Consequently, one single analysis will be conducted on all data available on participants from combined Stage 1 and Stage 2.

1.2 OBJECTIVE AND ENDPOINTS

The objectives and endpoints as defined in the protocol are summarized in Table 2.

Table 2 - Objectives and endpoints

	Objectives	Endpoints
Stage 1		
Primary		
	 To determine the effect of venglustat on the rate of TKV growth in patients at risk of rapidly progressive ADPKD 	 Annualized rate of change in TKV based on magnetic resonance imaging (MRI) from baseline to 18 months
Secondary		
 Efficacy objectives 	 To determine the effect of venglustat on the rate of renal function (eGFR) decline 	 Annualized rate of change in eGFR (CKD-EPI equation) from baseline to 18 months
	 To determine the effect of venglustat on pain and fatigue, based on patient reported diary 	 Change in pain from baseline to 18 months, based on BPI Item 3 assessed from the daily symptom diary
		 Change in fatigue from baseline to 18 months, based on BFI Item 3 assessed from the daily symptom diary
	 To evaluate the PK of venglustat in ADPKD patients 	Plasma venglustat concentrations
 Safety/tolerability objectives 	 To characterize the safety profile of venglustat 	 Treatment emergent adverse events (TEAEs)/adverse events (AEs)/serious adverse events (SAEs), laboratory parameters, vital signs, electrocardiogram and findings from physical examination
	 To evaluate the effect of venglustat on mood using BDI-II 	 Change in score of BDI-II during the treatment emergent period
	 To evaluate the effect of venglustat on the lens by ophthalmological examination 	 Change in the lens clarity by ophthalmological examination during the treatment emergent period
Tertiary/exploratory		
	 To explore the impact of venglustat on total liver volume (TLV) (in participants with height adjusted total liver volume htTLV >1 L/m) 	 Annualized rate of change in TLV based on MRI (in participants with htTLV >1 L/m) from baseline to 18 months

Objectives Endpoints To explore the effect of Change in urine osmolality from venglustat on kidney baseline to 18 months concentrating ability by Change in nocturia from baseline to assessing urine osmolality (in 18 months, based on patient reported participants not on diuretic) To explore the effect of Change in SBP/DBP during the venglustat on nocturia treatment emergent period To explore the effect of Change in biomarkers associated with venglustat on systolic blood ADPKD (eg, FGF23 and ADMA) from pressure (SBP) and diastolic baseline to 18 months blood pressure (DBP) Change in pain (BPI) from baseline to To explore the effect of 18 months venglustat on biomarkers Change in fatigue (BFI) from baseline associated with ADPKD to 18 months (eg, Fibroblast Growth Factor 23 Change in health status (EQ 5D 5L) [FGF23], Asymmetric from baseline to 18 months Dimethylarginine [ADMA]) Type, frequency, and dosage of To explore the effect of analgesic/over the counter (OTC) pain venglustat on pain (Brief Pain medication administration from Inventory [BPI]), fatigue (Brief baseline to 18 months Fatigue Inventory [BFI]), and Rate of all-cause hospitalization general health status (EuroQoL 5-dimension 5-level [EQ 5D-5L]) Change in Glucosylceramide (GL-1) to 18 months and GM3 from baseline to 18 months To explore the effect of venglustat on type, frequency and dosage of analgesic/over the counter (OTC) pain medication administration To explore the effect of venglustat on all-cause hospitalization To explore the pharmacodynamic (PD) effects of venglustat by measuring downstream metabolites of GCS in plasma and urine Stage 2 **Primary** Annualized rate of change in eGFR To determine the effect of venglustat on rate of renal (CKD-EPI equation) from baseline to function (eGFR) decline as 24 months compared to placebo in patients at risk of rapidly progressive **ADPKD**

	Objectives	Endpoints
Secondary		
 Efficacy objectives 	 To determine the effevenglustat on the rategrowth To determine the effevenglustat on pain anbased on patient reports 	of TKV based on MRI from baseline to 18 months ct of Change in pain from baseline to 24 months, based on BPI Item 3
		Change in fatigue from baseline to 24 months, based on BFI Item 3 assessed from the daily symptom diary
 Safety/tolera objectives 	 To evaluate the PK of in ADPKD patients To characterize the sa of venglustat 	TEAEs/AEs/SAEs, laboratory
	 To evaluate the effect venglustat on mood u 	
	 To evaluate the effect venglustat on the lens ophthalmological exar 	by ophthalmological examination during
Tertiary/exploratory		
	 To explore the impact venglustat on TLV (in participants htTLV >1 	based on MRI (in participants with
	To explore the effect of venglustat on kidney concentrating ability be assessing urine osmo participants not on divided.	Change in urine osmolality from baseline to 24 months Change in nocturia from baseline to 24 months, based on patient reported
	To explore the effect of venglustat on nocturial venglustat.	of Change in SBP/DBP during the
	 To explore the effect of venglustat on systolic pressure (SBP) and d 	• Annualized rate of change in mGFR blood from baseline to 24 months
	blood pressure (DBP) To explore the effect of	ADPKD (eg, FGF23 and ADMA) from
	venglustat on measur (mGFR) (substudy)	Change in pain (BPI) from baseline to 18 months
	 To explore the effect of venglustat on biomark associated with ADPK 	ters to 18 months
	(eg, Fibroblast Growth 23 [FGF23], Asymme Dimethylargining [ADI	ric from baseline to 18 months
	Dimethylarginine [ADI To explore the effect of venglustat on pain (Bright Inventory [BPI]), fatiguting the second	analgesic/over the counter (OTC) pain medication administration from baseline to 24 months
	Fatigue Inventory [BF]), and • Rate of all-cause hospitalization

Objectives Endpoints general health status (EuroQoL Change in Glucosylceramide (GL-1) 5-dimension 5-level [EQ 5D-5L]) and GM3 from baseline to 24 months to 24 months Annualized rate of change in eGFR To explore the effect of (CKD-EPI equation) from baseline to venglustat on type, frequency 24 months in participants with a and dosage of analgesic/over the screening eGFR between 30 and counter (OTC) pain medication 44.9 mL/min/1.73 m² administration To explore the effect of venglustat on all-cause hospitalization To explore the pharmacodynamic (PD) effects of venglustat by measuring downstream metabolites of GCS in plasma and urine To explore the effect of venglustat on eGFR (CKD-EPI equation) from baseline to 24 months in participants with a screening eGFR between 30 and 44.9 mL/min/1.73 m²

1.2.1 Estimands

Primary estimand defined for main endpoints are summarized in below Table 3. More details are provided in Section 4.

22-Jun-2021 Version number: 2

Table 3 - Summary of primary estimand for main endpoints

Endpoint	Estimands				
Category (estimand)	Endpoint	Population	Intercurrent event(s) handling strategy	Population-level summary (Analysis and missing data handling)	
Stage 1					
Primary objective: To	determine the effect of venglusta	at on the rate of TKV (growth in patients at risk of rapidly progressive A	ADPKD	
Primary endpoint (treatment policy)	Annualized rate of change in TKV based on MRI from baseline to 18 months	Stage 1 Intent-to- Treat (ITT)	regardless of adherence to study intervention	Difference in mean slope of log10-transformed TKV estimated from baseline to 18 months using a linear mixed effect model. Overall effect of venglustat assessed using a Multiple Comparison Procedure). No imputation of missing data	
Secondary objectives:	To determine the effect of veng	glustat on the rate of	renal function (eGFR) decline		
	To determine the effect of ven	glustat on pain and fa	itigue, based on patient reported diary		
Secondary endpoint (treatment policy)	Annualized rate of change in eGFR (CKD-EPI equation) from baseline to 18 months	Stage 1 ITT	regardless of adherence to study intervention	Difference in mean slope of eGFR estimated from baseline to 18 months using a linear mixed effect model. Overall effect of venglustat assessed using a Multiple Comparison Procedure).	
				No imputation of missing data	
Secondary endpoint (treatment policy)	Change in pain (BPI Item 3) from baseline to 18 months	Stage 1 ITT	regardless of adherence to study intervention	Overall effect of venglustat will be assessed using a Multiple Comparison Procedure using baseline adjusted least-squares means estimates at Month 18 from Mixed model with repeated measures (MMRM). No imputation of missing data	
Secondary endpoint (treatment policy)	Change in fatigue (BFI Item 3) from baseline to 18 months	Stage 1 ITT	regardless of adherence to study intervention	Analysis of fatigue will be identical to the one of pain	
Stage 2					
Primary objective: To	determine the effect of venglusta	at on rate of renal fun	ction (eGFR) decline as compared to placebo in p	patients at risk of rapidly progressive ADPKD	
Primary endpoint (treatment policy)	Annualized rate of change in eGFR (CKD-EPI equation) from baseline to 24 months	Combined Stage 1 and Stage 2 ITT	regardless of adherence to study intervention	Analysis of eGFR in Stage 2 will be identical to the one of Stage 1	

Endpoint			Estimands	
Category (estimand)	Endpoint	Population	Intercurrent event(s) handling strategy	Population-level summary (Analysis and missing data handling)
Secondary objectives	: To determine the effect of vengl To determine the effect of vengle		KV growth gue, based on patient reported diary	
Secondary endpoint (treatment policy)	Annualized rate of change in TKV based on MRI from baseline to 18 months	Combined Stage 1 and Stage 2 ITT	regardless of adherence to study intervention	Analysis not done as no post-baseline MRI data available on Stage 2 at the time of study discontinuation
Secondary endpoint (treatment policy)	Change in pain (BPI Item 3) from baseline to 24 months	Combined Stage 1 and Stage 2 ITT	regardless of adherence to study intervention	Analysis of pain in Stage 2 will be identical to the one of Stage 1
Secondary endpoint (treatment policy)	Change in fatigue (BFI Item 3) from baseline to 24 months	Combined Stage 1 and Stage 2 ITT	regardless of adherence to study intervention	Analysis of fatigue in Stage 2 will be identical to the one of Stage 1

2 SAMPLE SIZE DETERMINATION

In Stage 1, approximately 240 participants will be randomized (with randomization ratio 1:1:1) to placebo (n=80) or venglustat 8 mg (n=80) or venglustat 15 mg (n=80mg).

In Stage 2, approximately 320 participants with an eGFR between 45 and 89.9 mL/min/1.73 m² at screening will be randomized (with randomization ratio 1:1) to placebo (n=160) or venglustat (n=160).

In addition, 80 participants with an eGFR between 30 and 44.9 mL/min/1.73 m² at screening will be randomized (with randomization ratio 1:1) to placebo (n=40) or venglustat (n=40). The participants from Stage 2 with an eGFR between 30 and 44.9 mL/min/1.73 m² will not be included in the primary efficacy and safety analyses populations but the data from these participants will be analyzed separately.

This sample size will provide approximately 89% power to detect a 50% reduction in annualized rate of change in TKV at end of Stage 1 and approximately 87% power to detect a 30% reduction in annualized rate of change in eGFR between venglustat and placebo at the end of Stage 2. Overall, the total sample size will provide approximately 87% power to detect an effect on both TKV and eGFR.

Sample size and power calculations were based on simulations, assuming different scenarios regarding the dose-response relationship (Section 5.6.1). SAS program is provided in (Section 5.5). The following model parameters were estimated based on available datasets from a similar participant population (participants aged 18 to 50 years with Mayo class 1C-1E and baseline eGFR from 45 to 90 mL/min/1.73 m²) in 2 historical studies (Consortium for Radiologic Imaging Studies of Polycystic Kidney Disease (CRISP) and the Polycystic Kidney Disease Treatment Network ([HALT-PKD]):

- A slope of log10(TKV) of 0.02591, 0.02832 and 0.03141 in participants from Mayo class 1C, 1D and 1E respectively (corresponding to 6.1%, 6.7% and 7.5% increase per year in TKV), resulting in average slope of 0.02764 (6.6%/year) assuming 50% of 1C, 33% of 1D and 17% of 1E.
- Standard deviation for the residual error of TKV (on the log10 scale) of 0.02566 and standard deviation for the random effect of slope of 0.01477.
- A slope of eGFR of -3.16, -3.88 and -4.69 mL/min/1.73 m² per year in participants from Mayo class 1C, 1D and 1E respectively, resulting in average slope of -3.66 mL/min/1.73 m² per year assuming 50% of 1C, 33% of 1D and 17% of 1E.
- Standard deviation for the residual error of eGFR of 6.34 and standard deviation for the random effect of slope of 1.98.

In addition, sample size and power calculations assumed an overall significance level of 0.05 (2-sided), 10% dropout rate and included adjustments for handling of multiplicity of tests and futility analysis. Calculations were made using simulations (Section 5.5 and Section 5.6.1).

3 ANALYSIS POPULATIONS

The following populations for analyses are defined:

Table 4 - Populations for analyses

Population	Description
Screened	All participants who signed the Informed Consent Form (ICF).
Randomized	All participants from screened population who have been allocated to a randomized intervention by Interactive Response Technology (IRT) regardless of whether the intervention was received or not.
Exposed	All screened participants who took at least 1 dose of study intervention.
Population without trial impact (disruption) due to COVID-19	All randomized participants without any critical or major deviation related to COVID19 and who did not permanently discontinue treatment due to COVID19 and who did not permanently discontinue study due to COVID19
Stage 1 Intent-to-treat (ITT)	All participants randomized in Stage 1.
	Participants will be analyzed according to the intervention allocated by randomization (venglustat 15 mg, venglustat 8 mg or placebo).
Stage 1 Pharmacokinetic (PK)	All participants randomized in Stage 1 who took at least 1 dose of study intervention and who have at least one post-baseline PK assessment. Participants will be analyzed according to the intervention they actually received.
Stage 1 Pharmacodynamic (PD)	All participants randomized in Stage 1 who took at least 1 dose of study intervention and who have at least one post-baseline PD assessment. Participants will be analyzed according to the intervention they actually received.
Combined Stage 1 and Stage 2 ITT	All participants with an eGFR between 45 and 89.9 mL/min/1.73 m ² at screening who are randomized in Stage 1 or Stage 2.
	Participants will be analyzed according to the intervention allocated by randomization (venglustat 15 mg, venglustat 8 mg or placebo).
Secondary Stage 2 ITT	All participants with an eGFR between 30 and 44.9 mL/min/1.73 m ² at screening who are randomized in Stage 2. Participants will be analyzed according to the intervention allocated by randomization (venglustat 15 mg or placebo).
Extended Combined Stage 1 and Stage 2 Safety	All participants with an eGFR between 30 and 89.9 mL/min/1.73 m ² at screening who are randomized in Stage 1 or Stage 2 and who took at least 1 dose of study intervention. Participants will be analyzed according to the intervention they actually received.
Stage 2 Pharmacokinetic (PK)	All participants with an eGFR between 45 and 89.9 mL/min/1.73 m² at screening who are randomized in Stage 2, who took at least 1 dose of study intervention and who have at least one post-baseline PK assessment. Participants will be analyzed according to the intervention they actually received.
Combined Stage 1 and Stage 2 Pharmacodynamic (PD)	All participants with an eGFR between 45 and 89.9 mL/min/1.73 m ² at screening who are randomized in Stage 1 or Stage 2, who take at least 1 dose of study intervention and who have at least one post-baseline PD assessment. Participants will be analyzed according to the intervention they actually received.

Participants exposed to study intervention before or without being randomized will not be considered randomized and will not be included in any analysis population. The safety experience of these participants will be reported separately.

Randomized participants for whom it is unclear whether they took the study intervention will be considered as exposed and will be included in the safety population as randomized.

For any participant randomized more than once, only the data associated with the first randomization will be used in any analysis population. The safety experience associated with any later randomization will be reported separately.

For participants receiving more than one study intervention during the study, the intervention group for as-treated analyses will be the one to which the participant was treated with the longest duration.

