### **6.5.2 Rationale for study design and control groups**

This study is designed to demonstrate the efficacy by slowing the progression of kidney volume and concomitantly evaluate the effect on worsening renal function, patient reported outcome (PRO) and liver volume in patients with ADPKD. Due to the high variability of eGFR, the primary endpoint of Stage 1 is TKV growth rate while the primary endpoint in Stage 2 is the slope

of eGFR. Safety, tolerability, PK, and PD effects of venglustat are supported by Phase 1 and Phase 2 studies and animal toxicology data in rodents up to 26 weeks and dogs up to 39 weeks. In vitro and in vivo genotoxicity studies have been conducted and are negative. Carcinogenicity studies have not yet been conducted.

A prognostic enrichment approach is used to select patients for primary analysis population who will be at risk for rapid progression of disease based on those aged between 18 to 50 years, CKD Stages 2-3A, and Mayo Imaging Classification of ADPKD Class 1C-E. This enrichment allows the detection of treatment benefit on both TKV and GFR in the same population thus circumventing the need for performing separate trials in "early" and "late" ADPKD patients.

Patients with eGFR  $<45$  mL/min/1.73 m^2 aged 18 to 55 years old recruited in Stage 2 of the study will be not included in primary analysis population but the data from these patients will be analyzed separately.

Patients with CKD Stage 3b (eGFR 30 - 45 mL/min/1.73 m^2) aged 18 to 55 years old will be recruited in Stage 2 of the study to permit gathering information on venglustat in this severely affected patient population. However, this patient population will not be included in the Stage 2 primary analysis but will be analyzed separately. The rationale for including these patients in the study is to obtain further information on venglustat exposure, safety and efficacy in patients with lower renal function.

Based on the mode of action of venglustat the benefit of disease modification is expected to decrease whereas the exposures of venglustat increase with declining renal function. For this reason, CKD Stage 4 patients (eGFR  $<30$  mL/min/1.73 m^2) will not be included into the study.

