### 7.1 INCLUSION CRITERIA

I 01. Male or female adult with ADPKD with an age at the time the consent is signed:

- a) between 18 and 50 years (inclusive) for patients in Stage 1
- b) between 18 and 50 years (inclusive) for patients in Stage 2 with an eGFR between 45 and 89.9 mL/min/1.73 m^2 during the screening period\*
- c) between 18 and 55 years (inclusive) for patients in Stage 2 with an eGFR between 30 and 44.9 mL/min/1.73 m^2 during the screening period\*

Diagnosis of ADPKD in patients with a family history, will be based on unified Pei criteria (12). In the absence of a family history, the diagnosis will be based on the presence of renal cysts bilaterally, totaling at least 20, in the absence of findings suggestive of other cystic renal diseases.

I 02. Mayo Imaging Classification of ADPKD Class 1C, 1D, or 1E\*\* (3).

\*\*TKV volume must be confirmed by a central reader prior to Visit 3.

I 03. Estimated glomerular filtration rate between 45 and 89.9 mL/min/1.73 m^2 during the screening period\* (Chronic Kidney Disease Epidemiology Collaboration [CKD-EPI] equation) for Stage 1.

Estimated glomerular filtration rate between 30 and 89.9 mL/min/1.73 m^2 during the screening period\* (CKD-EPI equation) for Stage 2.

\*Eligibility will be confirmed by the eGFR value from one of the two first pre-randomization eGFR measurements (Visit 1 or Visit 2 measurements or Visit 1 and an additional measurement performed at the Investigator's discretion between Visit 1 and Visit 2).

I 04. Stable treatment regimen of antihypertensive therapy for at least 30 days prior to the screening visit for hypertensive patient.

I 05. Able to read, comprehend, and respond to the study questionnaires.

- I 06. Patient has given voluntary written informed consent before performance of any study related procedures not part of standard medical care.
- I 07. Patient does not have access to tolvaptan at the time of study start or tolvaptan is not indicated for treatment of patient according to treating physician (patient does not meet recommended criteria for treatment, refuses to initiate or does not tolerate treatment with tolvaptan).
- I 08. The patient, if female of childbearing potential, must have a negative blood pregnancy test ( $\beta$ -human chorionic gonadotropin [ $\beta$ -hCG]) at the screening visit and a negative urine pregnancy test at the baseline visit.

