## **8.3 BLINDING PROCEDURES**

### **8.3.1 Methods of blinding**

Venglustat and placebo to match venglustat will be indistinguishable from one another and be provided in identically matched packaging which includes labeling to protect the blind. In addition to maintain the blind, the same number of capsules will be taken daily by the patient for each dosing group in Stage 1 and Stage 2.

In Stage 1, patients on 8 mg dosing group will receive 2 capsules of 4 mg. Patients on 15 mg dosing group will receive 1 capsule of 15 mg, plus 1 placebo capsule. Patients on placebo dosing group will receive 2 capsules of placebo. Likewise, in Stage 2, patients on venglustat or on placebo will receive the same number of capsules.

In accordance with the double-blind design, study patients, Investigators and study site personnel will remain blinded to study treatment and will not have access to the randomization list (treatment codes) except under circumstances described in [Section 8.3.2](#). At the assay institutions charged for PK measurements, only samples collected from patients on active drug will be analyzed leading to unblinding of responsible bioanalysts prior to data base lock. Bioanalysts are excluded from the clinical study operation's team and a process will be set up to prevent any potential unblinding ie, no unblinded data will be shared with the clinical study operational team prior to database lock and unblinding of the study. The Investigators and the Sponsor will also be blinded to PK and biomarkers data. A Sanofi Clinical Supplies representative will remain unblinded throughout the study with respect to the study medication kits in order to provide the appropriate study drug to patients; however, sites and study teams must be blinded to PK and biomarker data throughout the study.

Refer to [Section 10.5](#) for suspected unexpected serious adverse drug reaction unblinding by the Sponsor.

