#### **9.2.2 Stage 2**

- Annualized rate of change in TKV based on MRI from baseline to 18 months.
- Change in Pain (BPI - Item 3) from baseline to 24 months, from the daily symptom diary.
- Change in fatigue (BFI - Item 3) from baseline to 24 months, from the daily symptom diary.
- Plasma venglustat concentrations.

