### **9.4.14 Pharmacokinetics**

#### **9.4.14.1 Sampling time**

Blood samples for plasma venglustat assessment will be collected from all patients according to the time points described below and as shown in the study flow charts (see [Section 1.3](#) and [Section 1.4](#)):

Based on collection of PK samples from an anticipated 640 patients (5 samples per patient in Stage 1 for 240 patients and 3 samples per patient in Stage 2 for 400 patients), approximately 2400 PK samples are expected from the study.

- Stage 1:
  - Day 1: 3 ( $\pm$ 1) hours post dose,
  - Month 1: Pre-dose and 3 ( $\pm$ 1) hours post dose,
  - Months 6 and 18: Pre-dose.
- Stage 2:
  - Month 1: Pre-dose and 3 ( $\pm$ 1) hours post dose,
  - Month 24: Pre-dose.

At visits when a post-dose PK sample is to be collected, patients should take the study drug on site.

For PK sample collected at end-of-treatment visit in case of premature treatment discontinuation, time of last dose and time of PK sample collected should be accurately recorded.

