## 11 STATISTICAL CONSIDERATIONS

### 11.1 DETERMINATION OF SAMPLE SIZE

In Stage 1, approximately 240 patients will be randomized (with randomization ratio 1:1:1) to placebo (n=80) or venglustat 8 mg (n=80) or venglustat 15 mg (n=80). In Stage 2, approximately 320 patients with an eGFR between 45 and 89.9 mL/min/1.73 m^2 at screening will be randomized (with randomization ratio 1:1) to placebo (n=160) or venglustat (n=160). In addition, 80 patients with an eGFR between 30 and 44.9 mL/min/1.73 m^2 at screening will be randomized (with randomization ratio 1:1) to placebo (n=40) or venglustat (n=40). The patients from Stage 2 with an eGFR between 30 and 44.9 mL/min/1.73 m^2 will not be included in the primary efficacy and safety analyses populations but the data from these patients will be analyzed separately.

This sample size will provide approximately 89% power to detect a 50% reduction in annualized rate of change in TKV at end of Stage 1 and approximately 87% power to detect a 30% reduction in annualized rate of change in eGFR between venglustat and placebo at the end of Stage 2. Overall, the total sample size will provide approximately 87% power to detect an effect on both TKV and eGFR.

Sample size and power calculations were based on simulations, assuming different scenarios regarding the dose-response relationship (see [Appendix J](#) for additional details). The following model parameters were estimated based on available databases from a similar patient population (patients aged 18 to 50 years with Mayo Class 1C-1E and baseline eGFR from 45 to 90 mL/min/1.73 m^2) in 2 historical studies (Consortium for Radiologic Imaging Studies of Polycystic Kidney Disease (CRISP) and the Polycystic Kidney Disease Treatment Network [HALT-PKD]):

- A slope of log10(TKV) of 0.02591, 0.02832 and 0.03141 in patients from Mayo Class 1C, 1D, and 1E respectively (corresponding to 6.1%, 6.7% and 7.5% increase per year in TKV), resulting in average slope of 0.02764 (6.6%/year) assuming 50% of 1C, 33% of 1D and 17% of 1E.
- Standard deviation for the residual error of TKV (on the log10 scale) of 0.02566 and standard deviation for the random effect of slope of 0.01477.

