### **11.3.3 Pharmacokinetics/pharmacodynamics analysis population**

The PK and PD populations will be defined as all patients who were randomized, received at least one dose of the double-blind IMP and who have at least one PK or PD assessment, respectively.

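### SAP Table 4 restricts the Stage 2 PK and combined PD populations to screening eGFR 45–89.9, so no planned concentration summary includes the 30–44.9 patients

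*SAP*

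**What the plan says.** Protocol 11.3.3 gives one definition for both sets: "The PK and PD populations will be defined as all patients who were randomized, received at least one dose of the double-blind IMP", with at least one PK or PD assessment respectively. It mentions no eGFR range.

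SAP Section 3, Table 4, splits these sets by stage. The Stage 2 PK population is "All participants with an eGFR between 45 and 89.9 mL/min/1.73 m² at screening who are randomized in Stage 2", with at least one dose and one post-baseline PK assessment. The Combined Stage 1 and Stage 2 PD population carries the same eGFR limit. The Stage 1 PK and PD populations state no limit, but criterion I 03 in Protocol 7.1 requires for Stage 1 "Estimated glomerular filtration rate between 45 and 89.9". SAP 4.8.1 assigns the concentration summaries to the PK populations, and SAP 4.8.2 assigns the GL-1 summary to the PD populations.

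On the 30–44.9 patients, Protocol 6.5.2 says they are enrolled "to obtain further information on venglustat exposure, safety and efficacy in patients with lower renal function". Protocol 11.1 says they "will not be included in the primary efficacy and safety analyses populations but the data from these patients will be analyzed separately", and SAP Section 2 repeats this. Protocol 9.2.2 lists "Plasma venglustat concentrations" among the Stage 2 secondary endpoints. Table 4 gives these patients their own efficacy set (Secondary Stage 2 ITT) and includes them in the Extended Combined Safety population (30–89.9). It has no PK or PD row for them.

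**The concern.** The limit of 45–89.9 belongs to the primary efficacy and safety populations. Applied to PK, it removes the patients in whom the protocol itself expects higher exposure: Protocol 6.5.2 says exposure rises as renal function declines.

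Protocol 6.5.1 supports exposure at lower renal function with a steady-state PBPK prediction for GFR 30–60, a single-dose renal-impairment study (AUC up to 1.33-fold in moderate impairment, 90% CI 1.09 to 1.62) and margins to NOAEL exposures. Concentrations under repeated dosing in patients below eGFR 45 are what this trial could add to that. Someone following the SAP exactly would collect and assay those samples and then leave them out of every planned summary table.

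GL-1 is a lesser matter. It is exploratory and is not named in the 6.5.2 rationale.

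**Working it through.** **1. Can a 30–44.9 patient enter any PK or PD set?**

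| Population in SAP Table 4 | Screening eGFR admitted | Source of the limit |
|---|---|---|
| Stage 1 PK, Stage 1 PD | 45–89.9 | eligibility (I 03) |
| Stage 2 PK | 45–89.9 | Table 4 definition |
| Combined Stage 1 and Stage 2 PD | 45–89.9 | Table 4 definition |

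No set admits one, and SAP 4.8.1 and 4.8.2 name no other set for the summaries.

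**2. The protocol's own sample count.** Protocol 9.4.14.1 plans 5 samples for each of 240 Stage 1 patients and "3 samples per patient in Stage 2 for 400 patients":

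240 × 5 + 400 × 3 = 1,200 + 1,200 = 2,400, which agrees with the stated figure of about 2,400.

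The 400 is 320 + 80 (Protocol 11.1), so the sampling plan counts the 30–44.9 patients.

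**3. PK share lost, at plan.** Protocol 8.3.1 says "only samples collected from patients on active drug will be analyzed", so the active arms are the right base.

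- Stage 2 active-arm patients: 160 + 40 = 200; omitted 40/200 = 20%.
- Stage 2 active-arm samples: 3 × 200 = 600; omitted 3 × 40 = 120; 120/600 = 20%.
- Stage 1 active-arm samples: 5 × (80 + 80) = 800.
- Whole trial: 800 + 600 = 1,400; 120/1,400 = 8.6%; 1,400 − 120 = 1,280 remain.
- The 120 are all of the planned active-arm samples from patients with screening eGFR below 45.

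**4. GL-1 share lost, at plan.** Placebo is summarised too, so all arms count: 240 + 400 = 640 patients, of whom 240 + 320 = 560 are kept. Omitted: 80/640 = 12.5%.

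**5. Effect of the early stop.** Stage 2 PK sampling is two samples at Month 1 and one at Month 24. The 30–44.9 patients became eligible with Amendment 04 (14 August 2019). The futility review was on 14 May 2021 and SAP version 2 is dated 22 June 2021, just over 22 months after that amendment. No such patient could have reached Month 24 by then. SAP 4.4.2.2 also reports no post-baseline Stage 2 MRI, which was due at Month 18; I take this to mean that no Stage 2 patient had reached that visit. At full enrolment the scheduled samples affected are then at most 2 × 40 = 80 out of 2 × 200 = 400, still 20%. Some further samples may exist, because a premature end-of-treatment visit includes the Visit 12 procedures (Protocol 10.3.4).

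**The case against.** The strongest case on the other side has five parts.

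- **The planned counts overstate the loss.** This stands for the number of samples: step 5 caps the scheduled ones at 80, not 120. The 20% share of Stage 2 active-arm patients and samples does not change. Month 1 samples do not depend on the trial running to term, and SAP version 2, written after the stop, still plans Stage 2 PK summaries (Table 14).
- **Sparse concentrations cannot test an AUC ratio or a NOAEL margin.** Correct. Protocol 9.4.14.4 says no PK parameters will be derived. A table by eGFR category would show only whether observed concentrations at the same dose and visit are higher below 45. That is still the question 6.5.2 raises.
- **The data can be used elsewhere.** Protocol 11.4.4 provides for individual reporting, and population PK may take renal function as a covariate. But SAP 4.8.1 does not repeat the individual reporting, and a listing is not a summary. Population PK is optional and reported outside the study report.
- **The commitment to separate analysis is worded for the primary efficacy and safety populations.** That is fair. It does not promise a PK table, but it gives no ground for excluding these patients from PK either. The firmer basis is Protocol 11.3.3 together with the exposure rationale in 6.5.2.
- **The limit may be deliberate.** The SAP version history records that the PK populations were updated, but the reason given concerns time points. Neither that entry nor SAP Appendix 2 mentions an eGFR limit on PK.

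**Conclusion.** The point holds. SAP Table 4 departs from Protocol 11.3.3 without saying so, and the result is that the 30–44.9 patients appear in no planned summary of concentrations or GL-1. It probably arose by carrying over the primary-population limit, although the documents do not show this.

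The PK part is the substance, because it touches a Stage 2 secondary endpoint and a stated reason for enrolling the subgroup. The PD part is a matter of consistency. The sizes in steps 3 and 4 rest on planned enrolment and full sampling. Actual numbers are not in the documents and are likely smaller. Because the analyses are descriptive, the efficacy conclusions are untouched. It should be corrected, but it does not threaten the trial's main results.

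**What to change.** In SAP Section 3, Table 4, add a Stage 2 PK population for screening eGFR 30–44.9 and, for consistency, a matching PD population. Alternatively, widen the existing Stage 2 PK and combined PD populations to 30–89.9. Either way, in SAP 4.8.1 and 4.8.2 present the descriptive summaries by dose and visit separately for 30–44.9 and 45–89.9.

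If the restriction is intended, state it in Section 3 as a departure from Protocol 11.3.3, with the reason.

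The cost is one or two table rows and a few extra descriptive tables, some with small counts. No new samples and no inferential analysis are needed.
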